10.2. Populations for Analyses

For purposes of analysis, the populations described in [Table AMBG.10.1](#) are defined.

Table AMBG.10.1. Analysis Populations in Study AMBG

Population	Description
Intent-to-treat (ITT) Population	All randomized/assigned patients. Patients will be analyzed according to the treatment to which they were assigned
Modified Intent-to-treat (mITT) Population	All randomized/assigned patients who received at least 1 dose of study treatment in Study AMBG, regardless of whether correct treatment was administered or whether protocol was followed, will be analyzed according to the treatment to which they were assigned.
Safety Population	Same as mITT Population
Per-Protocol (PP) Population	All mITT patients who are not deemed noncompliant with treatment, who do not have significant protocol deviations (defined in the SAP), and whose investigator site does not have significant GCP deviations that require a report to regulatory agencies (regardless of study period). Qualifications and identification of the specific significant protocol deviations that result in exclusion from the PP population will be determined while the study remains blinded, prior to the database lock
Pharmacokinetic Evaluable	All patients who received at least 1 dose of investigational product and have sufficient blood sampling to allow for pharmacokinetic evaluation

Abbreviations: GCP = good clinical practice; SAP = statistical analysis plan.

Four analysis cohorts have been defined ([Table AMBG.10.2](#)).

Table AMBG.10.2. Analysis Cohorts in Study AMBG

Cohort ID	Cohort	Description
1	Main cohort (mirikizumab induction responders)	Patients who are randomized and responded to mirikizumab induction dosing and then are rerandomized to 200 mg mirikizumab SC or placebo
2	Mirikizumab induction nonresponders	Patients who are randomized and did not respond to mirikizumab induction dosing and then are enrolled into Study AMBG
3	Placebo induction responders	Patients who are randomized and responded to placebo in induction study and then enrolled into Study AMBG
4	Placebo induction nonresponders	Patients who are randomized and did not respond to placebo in induction study and then enrolled into Study AMBG

10.3. Statistical Analyses

10.3.1. General Statistical Considerations

Statistical analysis of this study will be the responsibility of Lilly or its designee.

Both efficacy and safety analysis will be conducted on the modified intent-to-treat (mITT) population. The efficacy analysis of the primary endpoint and major secondary endpoints will be repeated for intent-to treat population and the per-protocol population in the main cohort (mirikizumab induction responders). Additional analyses may be performed as deemed appropriate.

For efficacy analysis, the baseline will be defined as the initial baseline value before the patient is randomized into the induction study (Study AMAN), unless otherwise specified. For safety analysis, the baseline will be defined as the visit at Week 12 value in the induction study and prior to enrollment in Study AMBG, unless otherwise specified.

Unless otherwise specified, the main efficacy and safety analyses will be conducted on the main cohort for patients who respond to mirikizumab induction dosing and then are rerandomized to 200 mg mirikizumab SC dosing or placebo. For other cohorts of patients, efficacy and safety will be descriptive without statistical testing.

Summary statistics for continuous variables may include mean, standard deviation, median, and minimum and maximum values. Categorical variables will be presented as counts and percentages. Unless otherwise specified, variables will be analyzed in the original scale on which they are measured. The parametric approach will be employed by default for statistical analysis, except when nonparametric analysis, such as by a rank-based method, is assessed to be more fitting. Additional exploratory analyses of the data may be conducted as deemed appropriate. All hypothesis tests of treatment effects will be 2-sided, unless otherwise stated.

For assessments of the primary endpoint and other categorical efficacy endpoints among induced responders, the CMH chi-square test will be used to compare mirikizumab and placebo with stratification factors: (a) previous biologic therapy failure (yes or no), (b) baseline corticosteroid use (yes or no), (c) region (North America/Europe/Other), and (d) induction remission status (yes/no). The CMH chi-square p-value and the relative risk along with its 95% 2-sided confidence interval (CI) will be provided. In addition, the absolute treatment difference in proportions will be provided along with the 95% 2-sided CI estimate. The differences between mirikizumab and placebo will also be tested separately using a logistic regression model that controls for the stratification factors. If deemed necessary, additional analyses of categorical efficacy variables may be conducted to address sparse data and/or small sample sizes.

Treatment comparisons of continuous efficacy and health outcome variables will be made using mixed-effects model of repeated measures (MMRM) analysis. When the MMRM model is used, the model includes: (a) treatment group, (b) previous biologic therapy failure (yes or no), (c) corticosteroid use (yes or no), (d) region (North America/Europe/Other), (e) baseline value in the model, (f) visit, (g) induction remission status (if analysis is among induced responders), and (h) the interactions of treatment-by-visit and baseline-by-visit as fixed factors. The covariance structure to model the within-patient errors will be unstructured. If the unstructured covariance matrix results in a lack of convergence, the heterogeneous Toeplitz covariance structure, followed by the heterogeneous autoregressive covariance structure will be used. The Kenward-Roger method will be used to estimate the denominator degrees of freedom. Type III sums of squares for the least squares (LS) means will be used for the statistical comparison; the 95% CI will also be reported.

Treatment comparisons of continuous efficacy and health outcome variables with a single post-baseline time point will be made using analysis of covariance with: (a) treatment group, (b) previous biologic therapy failure (yes or no), (c) corticosteroid use (yes or no), (d) region

(North America/Europe/Other), (e) baseline value in the model, and (f) induction remission status. Type III sums of squares for LS means will be used for statistical comparison between treatment groups. The LS mean difference, standard error, p-value, and 95% CI, unless otherwise specified, will also be reported.

Any change to the data analysis methods described in the protocol will require an amendment ONLY if it changes a principal feature of the protocol. Any other change to the data analysis methods described in the protocol, and the justification for making the change, will be described in the clinical study report (CSR). Additional exploratory analyses of the data will be conducted as deemed appropriate.

10.3.1.1. Missing Data Imputation:

While every effort will be made to reduce missing data, the missing data imputation methods described below will be used to provide a conservative approach for assessing efficacy endpoints when patients are permanently discontinued from study drug or otherwise have missing data.

- Nonresponder imputation (NRI): For analysis of categorical efficacy and health outcomes variables, missing data will be imputed using an NRI method. Patients will be considered a nonresponder for the NRI analysis if they do not meet the categorical response criteria, have missing clinical response data at a time point of interest, or take rescue dosing with mirikizumab prior to the time point of interest.
- Mixed-effects model of repeated measures: For continuous variables, the primary analysis will be MMRM with the missing at random assumption for handling missing data. This analysis takes into account both missingness of data and the correlation of the repeated measurements. The data collected after rescue medication will be censored in the primary analysis. No additional imputation methods will be applied to the MMRM analysis.

Sensitivity analyses, including additional methods of handling missing data or analyzing the data that may be required to satisfy regulatory needs will be specified in the SAP.

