Notes: All activities should be completed prior to any study drug administration unless otherwise stated. Last visit or ETV is last visit prior to entering long term extension Study AMAP or post-treatment follow-up. Post-treatment follow-up visits should only occur if the patient is not proceeding to long term extension Study AMAP or if they discontinue treatment in Study AMBG early.

- a V1 (Week 0) should occur no more than 14 days from the start of the Visit 5/Week 12 visit of Study AMAN.
- b Patients who discontinue study drug with last dose administered IV will return for an LV +16 week post-treatment follow-up visit without a 12 week follow-up. Patients who discontinue study drug with last dose administered SC will return for an LV + 12 week post-treatment follow-up visit without a 16 week follow-up.
- c Results from Week 12 of Study AMAN will be used for Week 0 of this study.
- d Activity to be performed on a subpopulation of patients. See Notes column in table.
- e These tests will be run from the “chemistry” sample.

Table AMBG.2.2. Schedule of Activities – Nonresponders from Induction Study

Procedure	Extended Induction			Open-Label Maintenance Period									Post-treatment Follow-up		Notes	
	V1	V2	V3	V4 ^a	V5	V6	V7	V8	V9	V10	V11	V997	801	802		
Week	0	4	8	12	16	20	24	28	32	36	40 LV	ETV	UV	LV +4	LV +12/16 ^c	
Day and/or Visit Interval Tolerance	1 ^b	29 +/-3	57 +/-3	85 +/-7	113 +/-7	141 +/-7	169 +/-7	197 +/-7	225 +/-7	253 +/-7	281 +/-7		N/A	+/-10	+/-10	
Informed consent	X															Patients may consent between the start of V5 of Study AMAN and before any procedures at V1/Week 0 are performed.
Inclusion and exclusion criteria	X															Can begin at Week 12 of induction and continue until dosing is initiated in Study AMBG.
Concomitant medication	X	X	X	X	X	X	X	X	X	X	X	X	X	X	X	
Review AEs	X	X	X	X	X	X	X	X	X	X	X	X	X	X	X	
Tobacco/nicotine use	X ^d			X			X				X	X				
IP Administration																
IWRS/Randomization	X															
Open-label mirikizumab extended IV dosing	X	X	X													
Open-label mirikizumab SC dosing				X	X	X	X	X	X	X						
Physical Examination																
Vital signs (T, BP, and PR)	X	X	X	X	X	X	X	X	X	X	X	X	X	X	X	
Weight	X ^d			X			X				X	X				
Physical examination	X ^d										X	X				
Evaluate for EIMs	X	X	X	X	X	X	X	X	X	X	X	X	X			See Section 9.1.3.2.
12-lead ECG	X ^d										X	X				
Laboratory Investigations																

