5.4. Scientific Rationale for Study Design

The Phase 3 clinical trial program of mirikizumab in patients with moderate-to-severe UC consists of the following studies:

- Study AMAN: An induction study with a 12-week treatment duration.
- Study AMBG: A maintenance study with a 40-week treatment duration.
- Study AMAP: An open-label long-term extension study.

Study AMBG is designed to evaluate the maintenance of efficacy with blinded 200 mg mirikizumab Q4W in patients induced into clinical response with mirikizumab during the 12-week induction study, Study AMAN. Study AMAN includes patients with moderate to severely active UC.

Randomized withdrawal of mirikizumab clinical responders from Study AMAN to either placebo or continuation of mirikizumab administered SC, will enable evaluation of the benefits of maintenance dosing of mirikizumab following induction dosing.

Because randomized withdrawal of mirikizumab clinical responders to placebo may precipitate secondary LOR, 300 mg mirikizumab IV rescue will be provided to LOR patients who lose response after patients have completed at least 12 weeks of the maintenance study. Loss of response will be defined based on symptomatic criteria (that is, SF and RB) confirmed by endoscopic criteria (see Section 5.1).

The 40-week duration of this study provides a total of 52 weeks of continuous therapy (induction and maintenance) for mirikizumab patients who complete the 12-week induction study. The 40-week duration of randomized withdrawal in the maintenance study is expected to provide

adequate time for separation of efficacy effects between mirikizumab and placebo arms based on the approximate 10-day half-life of mirikizumab.

The primary endpoint tests whether mirikizumab maintains clinical remission among patients who achieved clinical remission to induction treatment with mirikizumab. Clinical remission is a clinically relevant composite endpoint, as it combines symptomatic improvement as well as endoscopic remission (anti-inflammatory effect) in the individual patient.

Patients are allowed to remain on a stable background dose regimen of conventional UC therapies during the study, except for oral corticosteroids. Corticosteroid tapering using a standardized algorithm will be mandated per protocol for patients who achieve clinical response to study drug in Study AMAN, or with extended induction for nonresponders from Study AMAN (see Section 7.7).

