6.1. Inclusion Criteria

Patients are eligible to be included in the study only if they meet all of the following criteria at maintenance study baseline, unless specifically defined:

Informed Consent

- [1.] Have given written informed consent approved by the ethical review board (ERB) governing the site prior to any study-specific procedures being completed.

Patient Characteristics

- [2.] Have completed Study AMAN through the Week 12 visit (Visit 5) and have a Visit 5 MMS and have received at least 1 study drug administration without early termination of study drug.
- [3.] Are willing and able to complete the scheduled study assessments, including endoscopy and daily diary entry.

[4.] Contraception

[4a.] Male patients:

No male contraception required except in compliance with specific local government study requirements

[4b.] Female patients:

Women of childbearing potential:

- A. Must test negative for pregnancy prior to initiation of treatment as indicated by a negative urine pregnancy test at Visit 1/Week 0 of this study.

AND

- B. Must agree to either remain abstinent, if complete abstinence is their preferred and usual lifestyle, or remain in same-sex relationships, if part of their preferred and usual lifestyle, without sexual relationships with males. Periodic abstinence (for example, calendar, ovulation, symptothermal, or post-ovulation methods), declaration of abstinence just for the duration of a trial, and withdrawal are not acceptable methods of contraception.

OR

Must use 2 effective methods of contraception for the entirety of the study. Abstinence or contraception must continue following completion of study drug administration for 20 weeks

- i. 2 effective methods of contraception (such as male or female condoms with spermicide, diaphragms with spermicide or cervical sponges) will be used. The patient may choose to use a double barrier method of contraception. Barrier protection methods without concomitant use of a spermicide are not a reliable or acceptable method. Thus, each barrier method must include use of a spermicide. It should be noted that the use of male and female condoms as a double barrier method is not considered acceptable due to the high failure rate when these methods are combined.
- ii. Of note, 1 of the 2 methods of contraception may be a highly effective (less than 1% failure rate) method of contraception (such as combination oral contraceptives, implanted contraceptives or intrauterine devices).

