7.2. Method of Treatment Assignment

Assignment to treatment groups for patients entering Study AMBG as clinical responders will be determined by a computer-generated random sequence using an interactive web-response system (IWRS) in a double-blind manner. To achieve between-group comparability, patients will be stratified to these arms based upon biologic-failed status (yes or no), baseline corticosteroid use (yes or no), region (North America/Europe/Other), and induction remission status (yes or no). This stratification will be controlled by IWRS.

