10.1. Sample Size Determination

Assuming that 90% of patients complete Study AMAN (which is expected to randomize approximately 1160 patients), Eli Lilly and Company (Lilly) anticipates approximately 1044 patients will enroll in Study AMBG. It is expected that approximately 470 of these patients will enter Study AMBG as clinical responders to mirikizumab and then will be randomized 2:1 to 200 mg mirikizumab SC (approximately 313 patients) and placebo (approximately 157 patients). Among the expected 470 mirikizumab clinical responders, approximately 180 mirikizumab clinical remitters will be randomized to 200 mg mirikizumab SC (approximately 120 patients) and placebo (approximately 60 patients). This assumes that:

- The induction study (AMAN, which has a mixed population with approximately 50% biologic-failed patients) is expected to have an overall clinical remission rate of 23% and response rate of 60% with mirikizumab.
- 75% of induction patients receive treatment with mirikizumab, based on a 3:1 randomization ratio for the induction study.
- 10% dropout rate from induction to maintenance.

The primary endpoint, clinical remission at Week 40, will be assessed on patients who achieved clinical response to mirikizumab induction treatment. Assuming mirikizumab and placebo clinical remission rates of 47% and 27%, respectively, this study based on the 470 mirikizumab induction responders is expected to have >95% power to demonstrate that mirikizumab is superior to placebo by using a chi-square test with a 2-sided significance level of 0.05. In addition, the sample size is expected to provide adequate power (>80%) to demonstrate that mirikizumab is superior to placebo for endoscopic remission, histologic remission, and corticosteroid-free remission at Week 40, among responders to mirikizumab induction treatment by using a chi-square test with a 2-sided significance level of 0.05.

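### Low priority, efficiency only: the default models for continuous other-secondary endpoints omit the endpoint's own value at re-randomisation, which the study already schedules

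*Protocol*

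**What the plan says.** All references are to the Protocol; the SAP was not available for this point.

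- **Baseline.** Section 10.3.1, for efficacy: "the baseline will be defined as the initial baseline value before the patient is randomized into the induction study (Study AMAN), unless otherwise specified".
- **MMRM covariates** (Section 10.3.1). After treatment, biologic failure, corticosteroid use and region, the list runs "e) baseline value in the model, (f) visit, (g) induction remission status", then treatment-by-visit and baseline-by-visit interactions.
- **ANCOVA covariates** (Section 10.3.1, for variables with one post-baseline time point). The list ends "e) baseline value in the model, and (f) induction remission status".
- **Week 0 value.** Table AMBG.2.1, footnote c: "Results from Week 12 of Study AMAN will be used for Week 0 of this study". The footnote is attached to the Visit 1 entries for IBDQ, EQ-5D 5L, SF-36, WPAI:UC, hsCRP, fecal calprotectin and the modified Mayo review.
- **Guaranteed at entry.** Inclusion criterion 2 requires that patients "have a Visit 5 MMS and have received at least 1 study drug administration", so among these only the Mayo items are assured for everyone.
- **Remission flag.** Section 7.2 also uses it to stratify randomisation: "and induction remission status (yes or no). This stratification will be controlled by IWRS".
- **Status of the endpoints.** The Synopsis leaves other secondary endpoints outside the multiplicity scheme.

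**The concern.** The comparison starts at re-randomisation, after 12 weeks of active treatment in patients selected for response. Their disease state at that moment enters the default models only as remission yes or no. On the planned numbers, 470 − 180 = 290 of the 470 randomised are responders not in remission, and the flag cannot tell them apart. A Week 0 measurement of the same variable may predict Week 40 better than the pre-induction value does. Leaving it out may give wider confidence intervals than the collected data allow.

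Three endpoints are outside the point or only conditionally in it. Corticosteroid dose is already measured from maintenance baseline. Fatigue NRS has no scheduled Week 0 value (Appendix 7). Abdominal pain NRS is a daily diary item with no row in Table AMBG.2.1, so it is covered only if its AMAN Week 12 diary value is available.

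**Working it through.** **Planned numbers reproduced (Section 10.1).** 1160 × 0.90 = 1044; 1044 × 0.75 × 0.60 = 469.8 (stated 470); 1044 × 0.75 × 0.23 = 180.1 (stated 180). The split is "randomized 2:1 to 200 mg mirikizumab SC (approximately 313 patients) and placebo (approximately 157 patients"). Primary power at 47% vs 27% comes to 99.0%, consistent with the stated >95%; this point does not touch it. No precision or power figure is stated for the continuous endpoints.

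**Set-up (large sample, one time point, complete data).** Y is the Week 40 value, X0 the induction baseline, X1 the Week 0 value and R the remission flag, all with unit variance and oriented so that correlations are positive. With X0 in the model, analysing change or Y gives the same treatment effect. R marks the best 180/470 of a latent variable correlated λ with X1. Slopes are pooled across arms, and SE² = v₁/313 + v₀/157, where v is the residual variance in each arm.

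**Assumptions, not in the protocol.** λ = 0.5, 0.7, 0.9; r(X0,Y) = 0.1, 0.2, 0.3; r(X0,X1) = 0.2, 0.3, 0.4; r(X1,Y) set per arm. The central case is 0.7, 0.2, 0.3.

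**Flag.** 180/470 = 0.383. The normal density at that cut is 0.3817, and 0.3817/√(0.383 × 0.617) = 0.785. So corr(R,X1) = 0.7 × 0.785 = 0.550, corr(R,X0) = 0.3 × 0.550 = 0.165, and corr(R,Y) = 0.550 × r(X1,Y).

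**Central case, 0.5 in both arms.**
- Planned: v = 1 − (0.2² + 0.275² − 2 × 0.2 × 0.275 × 0.165)/(1 − 0.165²) = 0.900.
- With X1 (R then adds nothing): v = 1 − (0.2² + 0.5² − 2 × 0.2 × 0.5 × 0.3)/(1 − 0.3²) = 0.747.
- SE ratio √(0.747/0.900) = 0.911, a fall of 8.9%.

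**Central case, 0.5 on mirikizumab and 0.2 on placebo.**
- Planned: v₁ = 0.903, v₀ = 0.966, SE = √(0.903/313 + 0.966/157) = 0.0951.
- With X1: v₁ = 0.758, v₀ = 0.982, SE = √(0.758/313 + 0.982/157) = 0.0932, a fall of 2.0%.
- A pooled-variance SE would print √[0.833 × (1/313 + 1/157)] = 0.0893, where 0.833 = (313 × 0.758 + 157 × 0.982)/470. That is 0.958 of the true SE, against 0.989 in the planned model.

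**Change in SE**

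| r(X1,Y), mirikizumab/placebo | Central | Grid range |
|---|---|---|
| 0.3/0.3 | −2.4% | −1.2 to −3.6% |
| 0.4/0.4 | −5.1% | −3.0 to −7.2% |
| 0.5/0.5 | −8.9% | −5.8 to −12.2% |
| 0.5/0.3 | −3.9% | −2.1 to −5.6% |
| 0.4/0.2 | −1.6% | −0.6 to −2.6% |
| 0.5/0.2 | −2.0% | −0.8 to −3.2% |
| 0.5/0.1 | −0.5% | +0.3 to −1.3% |
| 0.5/0 | +0.7% | +0.2 to +1.4% |

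If X1 is useless in both arms, the SE rises about 0.1%. A finite-sample simulation (6,000 trials per setting) gave falls of 9.5%, 2.3% and 1.0% at 0.5/0.5, 0.5/0.2 and 0.5/0.1.

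**Missing Week 0 values.** With 5% missing, mean imputation keeps a fall of 8.2% (0.5/0.5) or 1.9% (0.5/0.2). Dropping those patients would by itself raise the SE by 1/√0.95 − 1 = 2.6%.

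**The case against.** The strongest reply is that nothing here is wrong. Change from induction baseline is a legitimate outcome, the models adjust for that baseline and for the stratification factors, and remission status already carries part of the Week 0 state. The SAP may add the covariate. The benefit is not established either: "Randomized withdrawal of mirikizumab clinical responders from Study AMAN to either placebo or continuation of mirikizumab administered SC" is the design, so a weaker correlation on placebo is plausible, and there the gain is small or absent. The addition also brings its own problem, since at 0.5/0.2 a pooled-variance test would run at about 6.0% two-sided type I error, against about 5.3% for the planned model.

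Much of this stands. It limits the point to an optional refinement and means the covariate should not go in without a variance option. It does not remove the point, because the protocol fixes explicit covariate lists and a relevant, already scheduled measurement is absent from both.

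The calculation also fits some endpoints poorly. The Mayo items are scored 0–3, and a patient in remission has RB 0 and SF and ES of 0 or 1 by definition, so the flag already carries much of their Week 0 state. The 10-visit MMRM concerns mainly SF, RB and their sum, and the calculation does not model censoring after rescue. Less gain should be expected there.

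A reader might infer that the planned comparison is biased, that the efficacy baseline is misdefined, or that confirmatory results are weakened. The documents support none of these. Leaving out a prognostic covariate does not bias a randomised comparison in a linear model. The baseline definition matches the stated change-from-induction endpoints. The primary and major secondary endpoints are binary and analysed by CMH.

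**Conclusion.** The point holds as a low-priority efficiency improvement. The default covariate lists omit the endpoint's own re-randomisation value, and that value is scheduled for the endpoints named. A modest gain is likely but not certain. Within the grid the SE falls about 1–12% for a common correlation of 0.3–0.5 and about 1–3% at 0.5/0.2. The largest loss found is a rise of about 1.4%, with 0.5 on mirikizumab and none on placebo. These sizes rest wholly on assumed correlations and on a Gaussian, complete-data, single-time-point calculation with one pooled slope. They cover the parametric default, not the rank-based alternative that Section 10.3.1 also permits. The planned models remain valid, and no multiplicity-controlled conclusion changes.

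**What to change.** Before unblinding, prespecify the following.

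1. Keep change from induction baseline as the outcome, and keep the induction baseline and remission status in the model.
2. **ANCOVA**, for endpoints whose scheduled post-baseline assessment is Week 40 (IBDQ, EQ-5D 5L, SF-36, WPAI:UC, hsCRP, fecal calprotectin, ES): add the Week 0 value of the same variable. Use a heteroscedasticity-robust SE or arm-specific variances, because slopes may differ after withdrawal.
3. **MMRM** (mainly SF, RB and their sum): add the Week 0 value with its visit interaction. Use an arm-specific covariance matrix in place of a robust SE, so that the Kenward-Roger degrees of freedom in Section 10.3.1 can be kept.
4. Set a treatment-blind rule for a missing Week 0 covariate, for example the mean across both arms, so that no patient is dropped.
5. Section 10.3.1.1 rules out further imputation in the MMRM. State that this refers to outcomes, so that it does not conflict with item 4.

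The cost is one more parameter per ANCOVA, about ten in the MMRM (ten visits, Weeks 4–40), the missing-covariate rule and the variance option. No new data are needed, and neither endpoint nor estimand changes. Section 10.3.1 asks for an amendment only when a principal feature changes, so an SAP entry should be enough.
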